Protocol summary and Chapter 8	This study has three groups, low dose group (2.5×10^{10} vp), middle dose group (5.0×10^{10} vp), and high dose group (1.0×10^{11} vp)	Protocol summary and Chapter 8	This study has three groups, low dose group (5×10^{10} vp), middle dose group (1.0×10^{11} vp), and high dose group (1.5×10^{11} vp)
Information of the 3rd Amendment			
Contents in Original Version (1.2)		Contents in Altered Version (1.3)	
Chapter	Original Contents	Page/Row	Altered Contents
Protocol summary and Chapter 8.2 Study endpoints	
 - Geometric mean titer of neutralizing antibody against SARS-CoV-2 on day 14, day 28, month 3, and month 6. - Seroconversion rate of neutralizing antibody against SARS-CoV-2 on day 14, day 28, month 3, and month 6. - Geometric mean fold 	Protocol summary and Chapter 8.2 Study endpoints	
 - Geometric mean titer of neutralizing antibody against SARS-CoV-2 on day 14, day 28, and month 6. - Seroconversion rate of neutralizing antibody against SARS-CoV-2 on day 14, day 28, and month 6. - Geometric mean fold

	increase of neutralizing antibody against SARS-CoV-2 on day 14, day 28, month 3, and month 6.		increase of neutralizing antibody against SARS-CoV-2 on day 14, day 28, and month 6.
Chapter 10.1 Participants screening	Urine pregnancy test (female only)	Chapter 10.1 Participants screening	HCG pregnancy test (female only)
Information of the 4th Amendment			
Contents in Original Version (1.3)		Contents in Altered Version (1.4)	
Chapter	Original Contents	Page/Row	Altered Contents
Chapter 9.4 Withdraw from the study	If a participant is infected by SARS-CoV-2 between day 0 and day 28 post-vaccination, immunogenicity data from he or she will not be included in analysis, but all SARS-CoV-2 infections occurred within 1 year after the vaccination should be documented and reported following the same procedure of SAE reporting.	Chapter 9.4 Withdraw from the study	If a participant is infected by SARS-CoV-2 between day 0 and day 28 post-vaccination, immunogenicity data from he or she will not be included in analysis, but all SARS-CoV-2 infections occurred within 6 months after the vaccination should be documented and reported following the same procedure of SAE reporting.

PROTOCOL SUMMARY

Brief Title	A phase I clinical trial of the recombinant novel coronavirus vaccine (adenovirus type 5 vector) in healthy adults
Official Title	A single-center, open-label, dose-escalating phase I clinical trial of the recombinant novel coronavirus vaccine (adenovirus type 5 vector) in healthy adults aged between 18 and 60 years in China.
Objectives	
Primary objective: To evaluate the safety and tolerability of the recombinant novel coronavirus vaccine (adenovirus type 5 vector) in healthy adults aged 18 to 60 years.
 
Secondary objective: To evaluate the immune response of the recombinant novel coronavirus vaccine (adenovirus type 5 vector) in healthy adults aged 18 to 60 years.

Target disease	To prevent COVID-19 caused by SARS-CoV-2
Target population	Healthy adults aged between 18 and 60 years
Sample size	108 participants
Rational and background	
The SARS-CoV-2 is an unsegmented single-stranded positive-strand RNA virus, which belongs to the subfamily of the family Coronaviridae. Six coronaviruses are known to be able to infect humans, including 229E, OC43, HKU1, NL63, Middle East Respiratory Syndrome associated coronavirus (MERS-CoV) and severe acute respiratory syndrome associated coronavirus (SARS-CoV). The SARS-CoV-2 is a novel coronavirus isolated from the secretions of lower respiratory tract of patients with unexplained pneumonia in Wuhan, which belongs to β genus. After the outbreak of SARS-CoV in 2002 and the outbreak of MERS-CoV in 2012, SARS-CoV-2 is the third highly pathogenic coronavirus found in humans in the past 20 years. Since the outbreak of COVID-19 in December 2019, it has caused a global public health emergency. Up to March 14, 2020, China has reported 81029 confirmed cases and a total of 3194 deaths. At present, there is no specific drug for COVID-19. The COVID-19 epidemic has brought heavy economic pressure and medical burden to China, which has seriously endangered the national security and public health.
 
The recombinant novel coronavirus vaccine (adenovirus type 5 vector) was jointly developed by the Beijing Institute of Biotechnology and CanSino Biologics Inc., to prevent COVID-19 caused by SARS-CoV-2 infection. The vaccine uses replication-defective human adenovirus type 5 as vector and

	
express the specific S protein of SARS-CoV-2, which is prepared by amplification and purification. Preclinical studies suggest that both humoral and cellular immune responses play important roles in protective immunity. This is a phase I clinical trial to evaluate the safety, tolerability and immunogenicity of recombinant novel coronavirus vaccine (adenovirus type 5 vector) at 5×10^{10}vp, 1×10^{11}vp and 1.5×10^{11}vp in healthy adults aged between 18 and 60 years old.

Investigational vaccine
	
The recombinant novel coronavirus vaccine (adenovirus type 5 vector): Manufactures: Beijing Institute of Biotechnology and CanSino Biologics Inc. 0.5ml/ vial. Batch number: 202003001C. Valid until: 2022.02.28. Dosage: 5×10^{10}vp, 1×10^{11}vp and 1.5×10^{11}vp
 
Immunization: intramuscular injection at the lateral deltoid muscle of the upper arm on day 0.
 
Temperature for storage and transportation: at 2-8 °C

Trial design
	
Study design: a single-center, open-label, dose-increasing study.
 
Sample size: according to the "Technical guidelines for Vaccine Clinical Trials" issued by the China FDA, the sample size of each vaccine dose group is about 20-30 participants. In this study, 36 participants will be involved in the low-dose group, the middle-dose group and the high-dose group, respectively. A total of 108 participants will be recruited.
 
Study process: This study is performed in three steps: first, the low dose group (5×10^{10}vp); then, the middle dose group (1×10^{11}vp); at last, the high dose group (1.5×10^{11}vp), with 36 participants in each group. The trial will be carried out step by step from the low dose group to the high dose group, and the participants will be recruited sequentially. During the study, if any safety problems of the vaccine is noted, recruiting process should be stopped. The participants will be screened before involved in the study, and all the contents of the study will be completed through 9 visits. Study groups and dose increasing process are shown in the following table.

	
  
 Dose-increasing steps	Study groups	No.	
   
 1	Low dose	36	
 
 2	Middle dose	36	
 
 3	High dose	36	
 
 Total	-	108	
  
 
 Infection during the study period: During the study period, participants with fever, cough and other respiratory symptoms should immediately visit the designated hospital (Guanggu Hospital affiliated to Tongji Hospital, Tongji Medical College, Huazhong University of Science and Technology) and inform the investigators. The pharyngeal swabs or sputum and anal swabs will be collected and CT or other imaging examinations will be performed to identify SARS-CoV-2 associated infection. If a COVID-19 case is confirmed during the clinical trial, the case investigation should be carried out. If the disease of the COVID-19 case is classified as severe or fatal, severe or fatal case investigation should be carried out. 
 
 In addition to SARS-CoV-2 nucleic acid detection, more than 20 kinds of pathogens will also be detected in the specimens for the differential diagnosis. 
 
 Duration of the study: It takes about 6 months for each participant to participate in the study, from recruiting to the last visit. Some participants may withdraw the study during the course of the study. 
	Dose-increasing steps	Study groups	No.	1	Low dose	36	2	Middle dose	36	3	High dose	36	Total	-	108
Dose-increasing steps	Study groups	No.														
1	Low dose	36														
2	Middle dose	36														
3	High dose	36														
Total	-	108														
Endpoints	
 Primary endpoint: Occurrence of adverse reactions within 7 days after vaccination. 
 
 Secondary endpoints: Safety: 
 
– Occurrence of adverse events (AE) within 28 days after vaccination. 
– Occurrence of serious adverse events (SAE) within 28 days after vaccination. 
– Occurrence of serious adverse events during the whole follow-up period (6 months). 
– Changes of safety laboratory measures (hemoglobin, white blood cell count, total lymphocyte count, platelets, creatinine, alanine transaminase, neutrophil, glutamic oxaloacetic transaminase, total bilirubin, and fasting blood 
															

glucose) on day 7.

Humoral immunogenicity:

- Geometric mean titer of antigen-specific antibody on day 14, day 28, month 3, and month 6 measured by ELISA.
- Seroconversion rate of antigen-specific antibody on day 14, day 28, month 3, and month 6 measured by ELISA.
- Geometric mean fold increase of antigen-specific antibody on day 14, day 28, month 3, and month 6 measured by ELISA.
- Geometric mean titer of neutralizing antibody against SARS-CoV-2 on day 14, day 28, and month 6.
- Seroconversion rate of neutralizing antibody against SARS-CoV-2 on day 14, day 28, and month 6.
- Geometric mean fold increase of neutralizing antibody against SARS-CoV-2 on day 14, day 28, and month 6.
- Geometric mean titer of neutralizing antibody against Ad5 on day 14, day 28, month 3, and month 6.
- Geometric mean fold increase of neutralizing antibody against Ad5 on day 14, day 28, month 3, and month 6.

For uncertain values: when calculating GMT, GMI and seroconversion of antibodies, if the antibody level is below the initial detection limit, half of the initial value will be taken; if the antibody level is greater than the maximum detection limit, the maximum dilution will be taken.

Cellular immunogenicity:

Cell-mediated responses on day 14, day 28, and month 6:

- Positive rate and level of IFN- γ measured by ELISpot.
- Intracellular cytokine staining (ICS) assay to measure positive rates and levels of IFN- γ , TNF α and IL-2 expressed by the active CD4+T and CD8+T lymphocyte.

Exploratory Endpoints

- The correlation between antigen-specific antibody measured by ELISA and neutralizing antibody against SARS-CoV-2.
- The dose-response relationship of antigen-specific antibody measured by ELISA across the dose groups.
- The persistence of the antigen-specific antibody measured by ELISA at month 6.
- The correlation between the initial time of the antibody response and the dose groups.
- The correlation between cell-mediated responses (ELISpot IFN- γ , and ICS positive rates of IFN- γ , TNF α and IL-2

	
expressed by the active CD4+T and CD8+T lymphocyte) and the dose groups.
 
 - The persistence of the cell-mediated responses (ELISpot IFN-γ, and ICS positive rates of IFN-γ, TNFα and IL-2 expressed by the active CD4+T and CD8+T lymphocyte) at month 6. - The correlation between the initial time of the cell-mediated responses (ELISpot IFN-γ, and ICS positive rates of IFN-γ, TNFα and IL-2 expressed by the active CD4+T and CD8+T lymphocyte) and the dose groups.

Scheduled site visits
	
This study has 9 scheduled visits, including V0 (within 7 days before the vaccination), V1 (day 0), V2 (day 3), V3 (day 7), V4 (day 10), V5 (day 14), V6 (day 28), V7 (month 3), V8 (month 6).
 
Chest CT scan and nucleic acid screening before the vaccination:
 
 - All the participants are examined by chest CT, and those with COVID-19 imaging features will be excluded. - Pharyngeal swabs or sputum and anal swabs are collected and detected by RT-PCR or/and NGS methods. Those with positive result will not be involved in the study. 
Humoral immune response:
 
 - V0 (within 7 days before the vaccination): blood will be collected and anti-S and anti-N protein specific IgM and IgG antibodies will be detected by chemiluminescent immunoassay. - V1 (before the first vaccination), V5 (day14), V6 (day 28), V7 (month 3) and V8 (month 6). 10ml of peripheral venous blood will be collected at each visit, and the serum antibodies will be detected by ELISA, neutralization test with SARS-CoV-2 and/or its pseudovirus. 
Cellular immune response:
 
 - V1 (before the vaccination), V5 (day 14), V6 (day 28), V8 (month 6), 20ml of peripheral venous blood will be collected at each visit, and the PBMC will be isolated to detect the level of specific T cell responses.

Criteria for pausing or early termination
	
The investigators will collect daily reports of adverse events after vaccination and report to the Data Safety Monitoring Board (DSMB) every day. The DSMB independently analyzes the post-vaccination safety data in each dose group. If an increased risk of participants is found in the course of the study, they send notice to the principal investigator and the sponsor immediately to suspend or terminate the recruiting of participants in clinical trial,

	
during the dose-escalating procedure. If there is a violation of the protocol, GCP or ethical requirements, the sponsor, the principal investigator, the ethics committee or the administrative department shall have the right to suspend or terminate the study, and shall notify other parties and participants and explain the reasons.
 
Administration of study injections and new enrollments will be paused, if:
 
 - One or more \geqgrade 4 adverse reaction or serious adverse event may be associated with vaccination, or - Occurrence of grade 3 adverse events associated with vaccination in 15% of participants or more (including injection-site reaction, systemic reaction, and change of the safety laboratory measures), or - Required by sponsor, or - Required by regulatory authority, or - Required by institutional review board (IRB). 
The study may come to an early termination, if DSMB, sponsor and investigator agree that the risk increased and the risk-benefit for participants is no longer reasonable.

Initial analyses
	
Initial analyses: After the last participants completed V6 (day 28), data on the safety, humoral immunogenicity and cellular immunogenicity will be allowed for initial analyses.
 
Final analyses: After the last participants completed V8 (month 6), data on the safety, humoral immunogenicity and cellular immunogenicity will be allowed for final analyses.


Inclusion criteria
	
 - Aged between 18 and 60 years. - Able to understand the content of informed consent and willing to sign the informed consent - Able and willing to complete all the secluded study process during the whole study follow-up period (about 6 months). - Negative in HIV diagnostic blood test - Axillary temperature $\leq 37.0^{\circ}\text{C}$ - Negative serum IgM and IgG to the SARS-CoV-2 - Chest CT scan is normal (no COVID-19 imaging) - Pharyngeal swabs or sputum and anal swabs are negative for SARS-CoV-2 - A body mass index (BMI) are between 18.5 and 30.0 - Indexes of blood routine, biochemistry and other laboratory tests are within the normal ranges, or not clinical significant

	
judged by doctors (including white blood cell count, lymphocyte count, neutrophils, platelets, hemoglobin, ALT, AST, total bilirubin, fasting blood glucose, creatinine)
 
 - General good health as established by medical history and physical examination.
Exclusion Criteria	
 - Family history of seizure, epilepsy, brain or mental disease - Participant that has an allergic history to any ingredient of vaccines - Woman who is pregnant, breast-feeding or positive in pregnancy test on day of enrollment, or is planning to be pregnant during the next 6 months - Any acute fever disease or infections - Have a medical history of SARS infection - Have serious cardiovascular diseases, such as arrhythmia, conduction block, myocardial infarction, severe hypertension and not well-controlled - Major chronic illness, such as asthma, diabetes, or thyroid disease, and not well-controlled - Hereditary angioneurotic edema or acquired angioneurotic edema - Urticaria in last one year - Asplenia or functional asplenia - Platelet disorder or other bleeding disorder may cause injection contraindication - Faint at the sight of blood or needles. - Prior administration of immunodepressant or corticosteroids, antianaphylaxis treatment, cytotoxic treatment in last 6 months - Prior administration of blood products in last 4 months - Prior administration of other research medicines in last 1 month - Prior administration of attenuated vaccine in last 1 month - Prior administration of subunit vaccine or inactivated vaccine in last 14 days - Being treated for tuberculosis - Any condition that in the opinion of the investigators may interfere with the evaluation of study objectives
Role of the sponsor	
Sponsors participate in the trial design and the protocol writing, but will not participate in other process of the trial, including data collection, statistical analysis, data interpretation and writing study report.

ABBREVIATIONS

AE	Adverse Event
AR	Adverse Reaction
Ad5	Replication Defective Human Adenovirus Serotype 5
CLA	Chemiluminescence Assay
COVID-19	Corona Virus Disease 2019
eCRF	Electronic Case Report Form
EDC	Electronic Data Capture
ELISA	Enzyme-linked Immunosorbent Assay
ELISpot	Enzyme-linked Immunospot Assay
FAS	Full Analysis Set
GCP	Good Clinical Practice
GMI	Geometric Mean Fold Increase
GMP	Good Manufacturing Practice
GMT	Geometric Mean Titre
IEC	Independent Ethics Committee
ITT	Intent-to-treat
MCPENT	Micro-CPE Neutralization Test
NIFDC	National Institute for Food and Drug Control
NMPA	National Medical Products Administration
PBMC	Peripheral Blood Mononuclear Cells
PPS	Per Protocol Set
SAE	Serious Adverse Event
SOP	Standard Operation Procedure
SS	Safety Set
vp	Virus Particle

TABLE OF CONTENTS

DOCUMENT HISTORY.....	2
PROTOCOL SUMMARY	4
1. OBJECTIVE AND INTRODUCTION.....	15
2. STUDY SITE	15
3. RELATED PARTIES IN CLINICAL TRIAL.....	15
3.1 Sponsor.....	15
3.2 Investigator.....	15
3.3 Contract Research Organization.....	16
3.4 Statistical Party.....	16
3.5 Clinical laboratory	16
4. BACKGROUND AND RATIONALE.....	17
4.1 Introduction of pathogen.....	17
4.2 Disease and Epidemiological background.....	18
4.3 Vaccine background.....	18
4.4 Advantages of this vaccine.....	25
5. PRECLINICAL STUDIES WITH CANDIDATE AD5-EBOV.....	26
5.1 Preclinical immunogenicity evaluation.....	26
5.2 Protective experiments in animals	31
5.3 Safety evaluation in preclinical research.....	35
5.4 Summary for preclinical studies.....	37
6. BRIEF INTRODUCTION OF PRODUCT CHARACTERISTICS.....	37
6.1 Production technology	37
6.2 Formulation.....	38
6.3 Stability research.....	38
6.4 Quality research and verification	39
6.5 Package	39
6.6 Transportation and Storage.....	40
7. STUDY OBJECTIVES.....	41
8. STUDY DESIGN	41
8.1 Design methods.....	41

8.2 Study endpoints	41
8.3 Study Procedures	43
8.4 Sample size.....	47
8.5 Criteria for pausing or early termination	47
8.6 Duration of study	48
9 PARTICIPANTS	48
9.1 Participants selection	48
9.2 Inclusion criteria	48
9.3 Exclusion criteria	49
9.4 Withdraw from the study	50
9.5 Complete of the study	51
9.6 Protocol violation and protocol deviation	52
10 METHODS AND PROCEDURES	54

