8. STUDY DESIGN

8.1 Design methods

This study is performed in three steps: first, the low dose group (5×10^{10} vp); then, the middle dose group (1×10^{11} vp); at last, the high dose group (1.5×10^{11} vp), with 36 participants in each group. The trial will be carried out step by step from the low dose group to the high dose group, and the participants will be recruited sequentially. The safety data will be evaluated every day, during the study, if any safety problems of the vaccine is noted, recruiting process should be stopped.

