8.5 Criteria for pausing or early termination

The investigators will collect daily reports of adverse events after vaccination and report the newly added adverse events to the Data Safety Monitoring Board (DSMB) in time. The DSMB independently analyzes the post-vaccination safety data in each dose group. If an increased risk of participants is found in the course of the study, they send notice to the principal investigator and the sponsor immediately to suspend or terminate the recruiting of participants in clinical trial, during the dose-escalating procedure. If there is a violation of the protocol, GCP or ethical requirements, the sponsor, principal investigator, ethics committee or administrative department shall have the right to suspend or terminate the study, and shall notify other parties and participants and explain the reasons.

Administration of study injections and new enrollments will be paused, if:

- One or more \geq grade 4 adverse reaction or serious adverse event may be associated with vaccination, or
- Occurrence of grade 3 adverse events associated with vaccination in 15% of participants or more (including injection-site reaction, systemic reaction, and change of the safety laboratory measures), or

- Required by sponsor, or
- Required by regulatory authority, or
- Required by institutional review board (IRB).

The study may come to an early termination, if DSMB, sponsor and investigator agree that the risk increased and the risk-benefit for participants is no longer reasonable.

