10.4 Safety observation

10.4.1 Methods of safety observation

After vaccination, all participants are required to stay in the designated temporary lodgment for a safety observe of 14 days and then they are allowed to be back to their home for further safety observation since day 15 post-vaccination. The contents of safety observation during the study period are as follows:

(1) After vaccination, the participants will stay at the clinic for 6-hour observation and the temperature will be captured by both wireless remote continuous temperature measurement system and routine axillary thermometer.

(2) Within 14 days after vaccination, the participants are asked to complete the safety observation by themselves, and record the results on the "diary card". A designated doctor is responsible for visit the participants every day and instruct them to complete the diary card.

(3) From the day 15 to the day 28 after vaccination, the participants will be instructed

to record any adverse events on the "diary card" by themselves. On day 28, the investigators visited the participants, retrospectively investigated and verified the contents of the safety observation.

(4) During the whole study period (about 6 months after vaccination), the participants will be asked to report any serious adverse events following the vaccination.

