10.4.6 Record of safety observation

Any clinically meaningful adverse event occurred after vaccination should be recorded in the diary card.

Verification and medical visits by investigator respond to adverse events are required,

such as investigation of medical history, physical examination and necessary laboratory examination (if required). Participants should receive appropriate medical treatment until the adverse event decline completed with complete records.

The record of adverse events should include the following:

- Description of adverse events
- Start and end time of adverse events
- Severity (grade)
- Relationship with vaccination
- Laboratory findings
- Treatment measures
- Outcome

If there are allergies, SAE, or a grade 3 adverse events or above happening in safety observation period, medical treatment should be provided until symptoms disappeared or stabilization of symptoms.

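### Daily adverse event reporting is stated with no end day, but from day 15 non-serious events other than fever, cough and respiratory symptoms have no stated route to the investigator before the day-28 visit

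*Protocol*

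**What the plan says.** Three places describe daily safety monitoring, none with an end day:

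- The Protocol summary, in its row on pausing and termination, states: "The investigators will collect daily reports of adverse events after vaccination and report to the Data Safety Monitoring Board (DSMB) every day".
- Section 8.1: "The safety data will be evaluated every day, during the study".
- Section 8.5 keeps daily collection by the investigators and has them "report the newly added adverse events to the Data Safety Monitoring Board (DSMB) in time".

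The pause criteria that follow in the summary and in 8.5 are one possibly related grade 4 reaction or serious adverse event, or related grade 3 events in at least 15% of participants. Neither carries a time limit.

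Section 10.4.1 describes how events are actually collected. For the first 14 days participants stay in designated lodging, and "A designated doctor is responsible for visit the participants every day and instruct them to complete the diary card". After that they go home. Item (3) begins "From the day 15 to the day 28 after vaccination, the participants will be instructed" and goes on to self-recording on the diary card. It ends: "On day 28, the investigators visited the participants, retrospectively investigated and verified the contents of the safety observation". Table 8-3-1-1 agrees: there is no visit between V5 (day 14) and V6 (day 28, ±3 days), and the second card is returned at V6.

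Two earlier routes exist after day 14. Section 10.4.1 item (4) asks participants to report serious adverse events throughout the roughly six months of follow-up. Section 10.5.6, and the paragraph on infection in the summary, send participants with fever, cough or other respiratory symptoms to the designated hospital at once and have them inform the investigators, whether or not the event is serious.

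**The concern.** The summary and sections 8.1 and 8.5 present daily information as the basis for pausing the trial. The procedure in 10.4.1 cannot supply it for days 15 to 28, because an event written only on a card at home is unknown to the investigator and so cannot be forwarded to the DSMB. The gap lies between participant and investigator. How fast the investigator forwards reports is a separate matter.

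Two things are at stake. First, the pause rule can count late events only once they are known. Second, section 10.4.6 states that "Verification and medical visits by investigator respond to adverse events are required", and it also calls for treatment of grade 3 or higher events. It gives no route or deadline by which an event on days 15 to 28 comes to the investigator's notice. The protocol itself names one relevant symptom: section 13.3.1 says that joint pain, seen with another vector vaccine, needs to be observed in this study. Arthralgia below the threshold for a serious event falls in the gap.

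**Working it through.** The plan states no figure for this lag, so there is none to reproduce. The inputs are the visit schedule in Table 8-3-1-1, the 28-day adverse event window in 8.2.2.1, the grading tables in 10.4.2.3 and the timeline in section 12.

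**Share of the window.** Days 15 to 28 are 14 days, and 14/28 = 50% of the secondary adverse event window. Day 28 is nominally V6 itself, so the days without scheduled contact are 15 to 27: 13/28 = 46%.

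**Lag from onset to V6.** For onset on day d, lag = V6 − d.
- Onset on day 15: 28 − 15 = 13 days nominally. Across the window it is 25 − 15 = 10 to 31 − 15 = 16 days.
- Even onsets on days 15 to 28, V6 on day 28: lags 13, 12, …, 0, mean (13 + 0)/2 = 6.5 days.
- The same onsets, V6 on day 31: lags 16, 15, …, 3, mean (16 + 3)/2 = 9.5 days.

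**Which events are exposed.**
- Fever, cough and other respiratory symptoms: covered by 10.5.6.
- Grade 4: many descriptors are hospitalization, life-threatening shock or disabling injury. These also meet the definition of a serious event in 10.4.2.1 and are covered by 10.4.1 item (4). A few, such as an injection-site abscess, need not be serious.
- Grade 3, non-serious, neither febrile nor respiratory: no stated route before V6. Examples are headache, fatigue, muscle pain, arthralgia, skin reactions and urticaria needing treatment.
- Safety laboratory results: after vaccination these are scheduled only on day 7, so none is delayed.

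**Pause rule count.** 0.15 × 36 = 5.4, so 6 participants if applied within a dose group. 0.15 × 108 = 16.2, so 17 if applied to all participants.

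**Overlap with dosing.** The table in section 12 is broken in the text at hand. If its 1 month (30 days) runs from first recruitment to the last V5 (day 14 ± 2), injections span about 30 − 14 = 16 days, with a range of 30 − 16 = 14 to 30 − 12 = 18. The first participant reaches day 15 when 0 to about 18 − 15 = 3 days of dosing remain. If instead the three groups opened two weeks apart (an assumption), the middle group would start with none of the low-dose group's exposed day 15 to 28 events known. That spacing needs at least 28 + 14 = 42 days to the last V5, longer than the 1 month indicated.

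**The case against.** The strongest reply has four parts.

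*The conflict is soft.* Section 8.5 speaks of forwarding new events, and a daily report of what is newly known need not mean daily contact with everyone to day 28. The power to suspend recruitment is also tied to the escalation phase. This is a possible reading, but the summary and 8.5 both have the investigators collecting reports daily, and nothing tells the reader that this ends at day 14.

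*Most dangerous events are covered.* This stands in large part. A reader might infer that no non-serious event can reach the investigator before V6, or that the pause rule is blind to all grade 3 and 4 events for half the window. The documents do not support that, given the respiratory and fever route and the overlap of grade 4 with serious events.

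*Dosing would be over.* On the section 12 timeline this is nearly right. That timeline is offered only for reference, however, and it lists completion of Visit 5 before the initial analysis, whereas 10.7.1.1 requires Visit 6. It cannot settle the question. The protocol fixes no interval between dose groups.

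*Care is assured elsewhere.* Section 13.3.2 requires immediate treatment for possibly related reactions of grade 3 or higher, and 10.4.7 requires treatment or consultation for reported events. Both depend on the event being known. The diary card and consent forms are not shown and may tell participants to call. The finding is therefore that the protocol states no route, not that none exists in practice.

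**Conclusion.** The concern holds in a limited form. The statements of daily collection and evaluation conflict with the collection procedure for days 15 to 28, half of the secondary adverse event window. The exposed events are mainly non-serious grade 3 events that are neither febrile nor respiratory, plus a few non-serious grade 4 events. An event with onset on day 15 waits 10 to 16 days, and the mean wait is 6.5 to 9.5 days for V6 on day 28 to day 31. The means assume even onsets on days 15 to 28 and no unprompted call by the participant.

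The primary endpoint (adverse reactions within 7 days) lies wholly inside the period of daily visits and is untouched. A reader might also infer that escalation decisions are taken on incomplete safety data. The documents do not show that: on the indicative timeline the cost is mainly to oversight and care, and it would reach escalation only if the groups were spaced further apart. The point should be corrected, but it does not threaten the main safety result.

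**What to change.** Reconcile the summary and sections 8.1 and 8.5 with section 10.4.1, in one of two ways.

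1. In 10.4.1 item (3), instruct participants to notify the investigator the same day of any event on days 15 to 28 that may reach grade 3 or higher under Tables 10-4-1-1 to 10-4-1-3, and have it forwarded to the DSMB under 8.5. The trigger should follow those tables, not a general phrase about limited activity: for fatigue, an effect on normal daily activities is only grade 2, and some grade 3 criteria are defined by size or frequency. A telephone check near day 21 is optional.
2. Otherwise, limit the daily statements to days 0 to 14, and state that from day 15 until V6 the pause rule does not see non-serious events outside the fever, cough and respiratory route.

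Neither option changes the pause thresholds. The cost is a few lines of wording and, under the first option, a few participant calls. No extra visit, sample or staff role is needed.
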